### **Data Analysis and Statistical Methods**

Direct study group comparison of the primary and secondary outcome variables will be performed using routine statistical tests utilizing a statistician at Tufts CTSI. In addition, the study will collect limited descriptive information pertinent to the effectiveness of visualizing superficial peripheral veins.

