In the clinical setting, NIR technology has shown to significantly increase the number of identifiable possible cannulation sites compared with normal eyesight [3,4]. However, the improvement in visualization did not automatically translate into improvement in successful cannulation of veins. Specifically, the efficacy of these vein finding devices has shown limited benefit when tested in the pediatric in-hospital population with a nonselective use in all patients. A meta-analysis of 11 RCTs concluded that using NIR light devices did not have an impact on overall failure rate at the first attempt at peripheral intravenous cannulation (PIVC) in pediatric patients [5]. Similarly, in studies evaluating the number of attempts required for successful PIVC found no difference between the NIR light device and traditional methods [6]. Many investigators subjectively felt the NIR device to be helpful; particularly in selected patients [5]. Yet, subgroup analysis did not define the cohort of pediatric patients that would benefit most from this technology. One publication interpreted these outcomes as such that despite improved visualization of superficial veins, successful venous puncture remains heavily dependent on the skills of the operator [7].

The efficacy of NIR vein finders beyond the first line approach, particularly in patients that have failed conventional peripheral venous access methods or in patients that are expected to be a “difficult stick”, is not established. Conflicting results have been reported in the pediatric literature regarding the subjective benefit of NIR light devices in patients with perceived difficult peripheral intravenous access [6]. In addition, knowledge about the efficacy of these devices in the adult inpatient setting is mostly unknown. The aim of the present study is to address these knowledge gaps.

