### **Eligibility Criteria**

The eligibility criteria were chosen to minimize the risk to the study patient by only including patients who are already planned to undergo placement of a peripheral venous catheter and by excluding any high-risk patients. In order to be considered for the study, patients have to meet the following criteria:

a) Inclusion criteria:

- adult in-hospital patients ( $\geq 18$  years of age, inpatient and outpatient setting)
- willing to provide research authorization
- scheduled and consented to undergo peripheral venous cannulation of one of the upper extremities to be performed by one of the members of the Vascular Access Team
- determined to be a difficult peripheral venous access defined by one of the following criteria in alignment to the A-DIVA scale to be assessed by one of the members of the Vascular Access Team [8]:
  - failed inspection for more than one visible or palpable suitable vein through conventional methods
  - failed at least one attempt of peripheral venous cannulation through any methods
  - history of difficult peripheral venous access
  - greatest diameter of target vein less than 3mm determined by conventional methods

b) Exclusion criteria:

- clinical contraindication for placement of peripheral venous catheter, including:
  - severe bilateral upper extremity edema
  - severe bilateral upper extremity skin burn
  - severe bilateral upper extremity cellulitis
  - history of bilateral axillary lymphadenectomy

- known severe cardiovascular or pulmonary compromise demanding minimization of procedure time, such as:
  - severe shock with severe cardiovascular instability
  - active CPR
  - major uncontrolled hemorrhage
  - any condition for which the primary healthcare provider is requesting emergent venous access
- scheduled PICC or midline catheter placement
- non-English-speaking patients if an interpreter is not available
- prisoner and any individual involuntarily confined or detained in a penal institution
- impaired capacity to make informed medical decisions

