### Peripheral Venous Cannulation and Randomization of Study Groups

Patients, who meet eligibility criteria and agree to participate in the study after an informed consent process, will undergo simple randomization. A sealed envelope holding the information of the random assignment will be opened by the Vascular Access Team member. Randomization will assign study patients into 1 of 3 groups/treatment arms with a 1:1:1 ratio:

- Placement of a peripheral venous catheter using conventional methods
- Use of VeinViewer to visualize the most suitable target. Once the target has been identified and marked, the device will be placed aside and the peripheral venous catheter will be placed using conventional methods
- Identification of the most suitable target and placement of a peripheral venous catheter under constant imaging with VeinViewer

When the VeinViewer device will be utilized, multiple areas on the patient's upper extremities will be assessed looking for the most suitable access point according to routine clinical practice. There is no restriction in regards to vein diameter, vein length, or relation of veins to joints. The choice of the location for intravenous cannulation, the use of tourniquets, the use of heating devices, and any techniques to palpate the vein will be left to the discretion of the Vascular Access Team member based on routine clinical practice. This study requires an unobstructed view of the subject's arm under standard hospital lighting conditions.

Investigators have up to 30 minutes or ONE attempt before the study allows for change of technique to the preference of the Vascular Access Team member.

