### **Data Collection**

*The following variables will be assessed for all study patients at the time of peripheral venous cannulation:*

a) primary outcome measures:

- rate of successful initial placement of a peripheral venous catheter (investigators have up to 30 minutes or ONE attempt before the study allows for change of technique to the preference of the Vascular Access Team member)

b) secondary outcome measures:

- number of required needle sticks before successful placement of a peripheral venous catheter
- type of method that resulted in successful placement of a peripheral venous catheter
- number of visible veins suitable for cannulation (each continuous vein will be counted as one cannulation site)
- IV catheter gauge size utilized after completion of IV cannulation
- target vein location (bend of the elbow, forearm, back of hand, other) and side of extremity (right vs. left)
- use of warming of arm
- procedure time
- procedure associated complications
- Vascular Access Team member experience (years in practice)
- Vascular Access Team member survey:
  - subjective difficulty locating a suitable vein
  - subjective difficulty of venous access
  - subjective reasons for the difficulty of identifying veins
  - subjective impression of locating additional veins with VeinViewer device
  - subjective impression of usefulness of the VeinViewer device in successful placement of a peripheral venous catheter
- Patient survey:
  - usual number of IV attempts required
  - patients' satisfaction after completion of IV cannulation

c) clinical patient demographics will be derived from patient history and/or medical records:

- age
- gender
- height

- weight
- dominant hand
- date of procedure

*The following variables will be assessed for all in-patient study subjects, if available, at the time of follow-up:*

- catheter patency / need for replacement of catheter / type of catheter used for replacement
- presence of complications such as :
  - hematoma
  - phlebitis
  - thrombophlebitis
  - infiltration
  - nerve damage

All abstracted data, including a study number for each patient, will be stored on a password-protected research database on a hospital server at Lahey Hospital & Medical Center. Any identifier, except for date of procedure, will be removed after the follow-up has been completed.

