### **Sample Size and Power Determination**

The study was designed such that we will need to enroll at least 125 patients per group (375 patients total for all three groups) to have 80% power if the estimated percentage with success in the control group is 50% and 70% in either of the study groups using a two-sided  $p < 0.0167$  for determining significance (study alpha was divide equally between the three groups).

We have therefore chosen to include 400 patients in the study. We anticipate that this initial data set will provide useful information regarding the effectiveness of the device in difficult access situations. In addition, it will give information about variability of data between patients that will guide the design of any future device and further studies that will answer more specific clinical questions.

Due to the need for appropriately trained staff to be available, the study will only be offered during hours when one of the trained Vascular Access Team members / co-investigators is available. During this time frame, the Vascular Access Team typically encounters approximately 50 patients per week. We anticipate that approximately 40% of these patients will meet study inclusion criteria. We estimate an approximate 60% study recruitment rate. We therefore expect that approximately 12 patients will be recruited into the study per week. The study is therefore estimated to be complete within 8 months.

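### The primary comparison appears unadjusted; naming baseline covariates already collected would give a small, nearly free gain in precision

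*Combined protocol and SAP*

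**What the plan says.** - **Analysis.** The section Data Analysis and Statistical Methods states: "Direct study group comparison of the primary and secondary outcome variables will be performed using routine statistical tests". It names no test, effect measure, model or covariate.
- **Sample size.** Sample Size and Power Determination rests on two success proportions, with the "estimated percentage with success in the control group is 50% and 70% in either of the study groups". It uses two-sided p < 0.0167 and 80% power, and arrives at 125 per group (375 in total), raised to 400.
- **Allocation.** Patients "will undergo simple randomization" in a 1:1:1 ratio, with no stratification factors.
- **Data.** The Data Collection section lists operator experience in years and, within the patient survey, the "usual number of IV attempts required". Both stand under secondary outcome measures. Height and weight are listed as demographics.
- **Eligibility.** Patients qualify by any one of four difficulty criteria, for example "failed at least one attempt of peripheral venous cannulation through any methods". These are judged before randomisation, but the criterion met is not among the variables to be recorded.
- **Background.** On pediatric trials, and with operator skill in mind, the section Near-infrared Superficial Vein Imaging says: "One publication interpreted these outcomes as such that despite improved visualization of superficial veins, successful venous puncture remains heavily dependent on the skills".

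**The concern.** First-attempt success in a difficult-access population may depend on who places the catheter and on how hard the patient usually is to cannulate. If so, an analysis that ignores both leaves explainable variation in the error term. Simple randomisation does nothing to balance them by design. Adjustment for values fixed before randomisation can tighten the arm comparison without extra patients, and naming the covariates in advance prevents their being chosen once results are known.

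There is also a problem of classification that needs no assumption. The plan promises between-arm comparison of the secondary outcome variables. Read literally, it would test operator seniority and patient history between arms, and those tests say nothing about the device.

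**Working it through.** **1. Reproduce the plan's figure.** Inputs from Sample Size and Power Determination: p0 = 0.50, p1 = 0.70, two-sided alpha 0.0167 (z = 2.393), power 80% (z = 0.842). The pooled proportion is 0.60.

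n = [2.393 × √(2 × 0.6 × 0.4) + 0.842 × √(0.25 + 0.21)]² / 0.20² = (1.658 + 0.571)² / 0.04 ≈ 124.2, so 125 per group. The plan's figure is reproduced by an unadjusted, pooled comparison without continuity correction (135 with correction). This supports reading the planned test as unadjusted.

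**2. Power as planned.** Power = Φ[(0.20√n − 1.658) / 0.678].

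- n = 125: Φ(0.852) = 80.3%
- n = 133 (400/3, rounded down): Φ(0.956) = 83.0%

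**3. Gain if the covariates explain a share R² of outcome variance.** R² is not in the documents and is assumed here. Effective n = n / (1 − R²), starting from 400/3 per arm and 83.2%:

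| R² | Effective n per arm | Power |
|---|---|---|
| 0.02 | 136.1 | 84.0% |
| 0.05 | 140.4 | 85.3% |
| 0.10 | 148.1 | 87.4% |

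That is about 1 to 4 points, equivalent to 2% (1/0.98) to 11% (1/0.90) more patients.

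**4. Gain with the fields actually collected.** They are imperfect proxies, so a simulation was built around them. All of the following are assumptions: 8 operators; operator and patient effects with SD 0 to 0.8 each on the logit scale; years in practice and usual attempts correlating 0.3 to 0.5 (r) with the true effects; BMI uninformative. There were 133 per arm, one imaging arm against control, success fixed at 50% and 70%, and 6,000 trials per row. The unadjusted pooled z-test is compared with a logistic Wald test using (A) years, attempts and BMI, or (B) operator identity, attempts and BMI.

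| Operator SD / patient SD, r | Unadjusted | A | B |
|---|---|---|---|
| 0 / 0 | 82.9% | 83.1% | 83.0% |
| 0.3 / 0.3, 0.3 | 82.8% | 83.0% | 83.4% |
| 0.5 / 0.5, 0.3 | 83.4% | 83.5% | 84.9% |
| 0.5 / 0.5, 0.5 | 83.2% | 84.4% | 85.5% |
| 0.8 / 0.8, 0.3 | 83.5% | 84.6% | 86.7% |
| 0.8 / 0.8, 0.5 | 83.6% | 85.4% | 87.4% |

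Gains are 0.1 to 1.8 points for A and 0.1 to 3.8 for B, with a Monte Carlo standard error of 0.2 to 0.4 points. Gains of 4 to 8 points appeared only with operator identity plus a perfectly measured patient covariate, which the plan does not collect.

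**5. Type I error (nominal 0.0167, Monte Carlo SE about 0.002).** Unadjusted 0.018 to 0.019; A 0.0175 to 0.018; B 0.019 to 0.021.

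**6. Standardised risk difference.** A further simulation of version A gave 0 to 2 points for the logistic test and 1 to 3 for the risk difference, with type I error of 0.010 to 0.021. Part of the larger figure probably comes from the variance formula and not from the covariates. An unpooled test with no covariates at n = 133 already has power Φ(0.20 × √133 / 0.678 − 2.393) = Φ(1.008) ≈ 84.3%, which is 1.3 points above the pooled 83.0%.

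**The case against.** The strongest reply is that nothing here is broken. The unadjusted test is valid, 400 patients exceed the 375 required, and the recommended version gains very little. Going from 125 to 133 per arm adds 2.7 points, so a gain of at most 1.8 is worth at most about 5 patients per arm (1.8 / 2.7 × 8). The smallest gains lie within simulation error. Every input to the size is assumed, and range may be restricted: all patients are difficult-access cases and all operators are trained team members with at least 20 prior uses. All of this stands, and it is why the point is only one to consider.

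Some narrower objections stand in part:

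- **Timing.** Usual attempts is not clearly a baseline value, because the plan gives no time for the question. Asking it before allocation is known resolves this.
- **BMI.** No passage calls it a predictor. It is included because it costs nothing to collect, and could be dropped.
- **Operator identity.** It is not collected, and its type I error ran up to about two standard errors above nominal. It should stay optional.
- **Labelling.** The stated secondary objectives do not cover operator experience or usual attempts, so their position may be list layout. The analysis sentence still commits to comparing whatever is listed as a secondary outcome.
- **A larger gap.** The plan names neither the primary test nor the set of contrasts. That is true, and whoever writes that paragraph can name the covariates in it.

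**Conclusion.** The concern holds as an optional improvement. The plan describes an apparently unadjusted comparison while collecting plausible baseline predictors, two of them filed as outcomes. With the collected fields the gain is about 0 to 2 points of power on the logistic test, and up to 3.8 if operator identity is added. These figures rest on the assumed operator and patient variation and proxy correlations set out above. If the predictors prove weak, power is unchanged (82.9% unadjusted, 83.1% adjusted). Operator skill is a plausible predictor here and not a proven one, since the plan's only support is one publication's reading of pediatric trials. The case for reclassifying the two fields does not depend on any of these assumptions.

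**What to change.** **Data Analysis and Statistical Methods (one paragraph).**

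- Make the primary analysis a logistic regression of first-attempt success on randomised arm, adjusted for operator years in practice, usual number of IV attempts and BMI, with the form of each term stated.
- List the arm contrasts, test each at 0.0167, and report a standardised risk difference with a matching confidence interval.
- State a simple rule, blind to arm, for filling missing covariates, including patients who have no usual number of attempts, so that no randomised patient leaves the model.
- Keep the unadjusted comparison as a sensitivity analysis.
- Do not adjust for number of visible veins, vein location, catheter gauge or warming, which are recorded at cannulation and may depend on the arm.

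**Data Collection.** Move years in practice and usual attempts from secondary outcomes to baseline covariates, and ask the usual-attempts question before the envelope is opened.

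**Optional.** Record operator identity (pooling low-volume operators) and which eligibility criterion was met, at one field each.

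**Cost.** The basic version needs no extra patients and no new fields. The one downside is a model in place of a 2×2 test.

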## **Study Monitoring and Safety Plan**

### **Study Monitoring**

After the first patient has been enrolled, the principle investigator will review the collected data every four weeks with other members of the study staff. At each research meeting, the principle investigator will evaluate study progress and assess protocol compliance. This will include the informed consent procedure, compliance with eligibility criteria, and identification of protocol violations. The principle investigator will also review all collected data to verify data accuracy, consistency, and integrity. The patients will be physically evaluated 3 days after the procedure by a Vascular Access Team member according to routine practice, unless discharged home or otherwise not available in-hospital, to assess for procedure related adverse events. The principle investigator will review any reports that could be pertinent to a potential adverse event. The principle investigator will be responsible for reviewing data from any adverse event and determining, if applicable, whether the research should be altered or stopped. Any decision to alter or stop enrollment will be reported to the IRB.

Any untoward medical event considered related or possibly related to study participation will be considered an adverse event. Serious adverse events (SAE) will be defined as stated in the IRB SAE reporting policy. Adverse events will be graded for severity according to NCI-CTCAE (version 4.0). For the purpose of safety reporting, the study period will be considered from the day of the procedure to the day of the last follow-up. All adverse events of grade II or greater attributable to study participation will be reported to the IRB. Multiple occurrences of an adverse event that, based on an aggregate analysis, is determined to be an unanticipated problem independent of the severity grade will be reported to the IRB. Any SAEs related to study participation will be reported within 5 business days of the PI learning of the event.

### **Protection of Human Subjects**

Non-invasive vein visualization devices are FDA class 1 devices (CFR title 21 section 880.6970). The VeinViewer Flex device (Christie Medical Holdings, Inc., Memphis, TN) used for this study is registered with the FDA for the intended use to indicate the location of blood vessels (<https://www.accessdata.fda.gov/scripts/cdrh/cfdocs/cfRL/rl.cfm?lid=241896&lpcd=KZA>). The device will be used in accordance with its labeling (IDE exempt under CFR title 21 section 812.2(c) category 2). Using the VeinViewer in the setting outlined in the inclusion criteria would represent standard of care (i.e. each study arm represents a form of standard of care currently practiced at Lahey Hospital & Medical Center). With the use of NIR light, the patient is not exposed to any significant energy or potential for harm. We therefore conclude that the proposed device is a **non-significant risk device qualifying for an IDE exemption**.

### **Risks**

Complications associated with peripheral venous access placement such as hematomas, phlebitis, thrombophlebitis, infiltration, and nerve damage can occur. However, since only patients will be included who under best medical practice would

undergo placement of a peripheral venous cannula anyhow, the potential added research risk to the study patients is minimal. Specifically, the risk of complications during peripheral venous cannula placement with the use of the VeinViewer is thought to be not greater than with the use of regular eyesight. The risk of the VeinViewer disturbing the flow of patient care is also felt to be insignificant due to the exclusion of patient's demanding minimization of procedure time.

Concerning the clinical patient information collected in the research database, all patient identifying information will be kept to a minimum and will only include medical record number and date of procedure. Furthermore, the data abstracted will be stored in a password-protected hospital server. No patient identifiers will be sent outside of Lahey Hospital, published, or be provided to anyone outside of the research team. Patient identifiers, except for date of the procedure, will be discarded after the last follow-up.

We therefore conclude that the proposed study represents **minimal risk**.

### **Benefits and Alternatives**

At present, insufficient evidence exists to characterize the effectiveness of this imaging technique; particularly in the setting of a difficult peripheral venous access. Therefore, study participation does not provide any proven benefit to the patient.

Apart from not participating in the study and pursuing standard/routine treatment options, there are no alternative options for any potential study patient. The patient's participation in this research study is voluntary. At any time, he or she may choose not to participate in this research study simply by contacting the principal investigator or a study team member. If the patient decides to withdraw consent to participate in the study after placement of the peripheral venous cannula, no new data about the patient will be collected for study purposes unless the data concerns an adverse event related to the study. Yet, all data that has already been collected for study purposes will continue to be used and analyzed.

